9.2. Criteria for Study Discontinuation

Patients may be withdrawn from the study if:

- The patient requests withdrawal
- If the patient develops side effects that are considered life-threatening
- If the patient refuses to have treatment as recommended
- If the patient refuses to have tests that are needed to determine whether the treatment is safe and effective
- If the agents used in this study cease to be available
- If other causes prevent continuation of the study
- For any other reason that the physician feels it may be necessary that the patient discontinue the study

10. STATISTICAL METHODS AND ANALYSES

10.1. Analysis Population

All treated subjects

10.2. Endpoints

10.2.1. Primary Endpoint

The primary endpoint is to estimate the proportion of patients that are alive and off all systemic IST at 12 months following initiation of treatment. To meet this endpoint, patients need to remain off IST for at least 8 weeks after discontinuing systemic immunosuppression (e.g. sirolimus). The use of rituximab and ibrutinib are not considered IST for this endpoint.

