Objectives:	
Primary Objective:
 
Efficacy The primary endpoint is to estimate the proportion of patients that are alive and off systemic immunosuppression therapies (IST) at 12 months following initiation of treatment. To meet this endpoint, patients need to remain off IST (e.g. sirolimus, tacrolimus, steroids, etc). for at least 8 weeks. The use of rituximab and ibrutinib are not considered IST for this endpoint.
 
Secondary Objectives:
 
Efficacy
 
To estimate:
 
 1. Chronic GVHD response (CR + PR, both individual organ response and overall response, according to 2014 NIH Response Criteria Working Group Report) – See Appendix G. 2. Cumulative steroid exposure (total mg methylprednisolone or equivalent). 3. Time to discontinuation of systemic immunosuppression, defined as the date that all systemic IST such as sirolimus, tacrolimus, steroids, etc. have been discontinued after resolution of all reversible manifestations of cGVHD. The use of rituximab and ibrutinib are not considered IST for this endpoint. Discontinuation of immunosuppressive medications for the purpose of inducing an anti-tumor response after the development of recurrent or secondary malignancy will not be counted as successful discontinuation of IST.

	
 4. Failure-free survival (defined as being alive without the requirement for second-line cGVHD therapy). See section 6.3 for definition of second-line cGVHD therapy. 5. Non-relapse and overall mortality 
Safety
 
To estimate:
 
 1. Incidence of grade ≥ 3 adverse events, possibly or probably related to either ibrutinib and/or rituximab.
Study Design:	This is an open-label, Phase 2 study designed to evaluate the safety and efficacy of ibrutinib and rituximab as primary treatment of cGVHD.
Population:	35 patients
Centers:	One

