In a completed phase II trial, our group tested rituximab in the upfront treatment of patients with cGVHD, and the results of this study were recently published in *Biology of Blood and Marrow Transplantation: Corticosteroid-Free Primary Treatment of Chronic Extensive Graft-versus-Host Disease Incorporating Rituximab* (Solomon, Sizemore et al. 2015). We hypothesized that the early use of rituximab would allow for more rapid discontinuation of immunosuppression while obviating the need for long courses of systemic corticosteroids, which would translate into reduced treatment-related morbidity and mortality associated with cGVHD.

Twenty-five patients (median age 56 years [range 29 – 77]) with extensive cGVHD were enrolled on a prospective phase II trial at our institution. Enrollment was limited to patients with first onset extensive cGVHD requiring systemic immunosuppression and without residual or concurrent acute GVHD. All patients received Rituximab 375mg/m² x 4 weekly doses, then one dose q3months x 4 doses. Twenty-two of 25 patients (88%) responded to treatment. Of the 22 responding patients, median time to maximum response was 161 days (range 35 – 300 days) with maximum response being complete in 21/22 patients and partial in 1 patient. Corticosteroids were used sparingly or not at all in the majority of patients. Immunosuppression was discontinued in 17 of 22 evaluable patients (77%) with median time to discontinuation of 300 days (range 138 – 488 days). With a median f/u of 27 months, estimated 2-year overall survival is 82%. Following immunosuppression discontinuation, cGVHD did recur in 7 patients after a median of 166 days (range 21-393 days), requiring reinstitution of systemic immunosuppression. When patients were analyzed 12 months following treatment initiation, 56% were alive, free of active GVHD, and off all systemic immunosuppression.

1.1.3. Targeting the Bruton's tyrosine kinase (BTK) and IL-2 inducible T-cell kinase (ITK) pathways with Ibrutinib for the treatment of cGVHD

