2. STUDY OBJECTIVE

2.1. Primary Objective

The primary objective is to evaluate the efficacy of the combination of rituximab and ibrutinib versus the historical experience with rituximab alone in the upfront treatment of cGVHD. The primary efficacy endpoint is to estimate the proportion of patients that are alive and off IST at 12 months following initiation of treatment. To meet this endpoint, patients need to remain off IST (e.g. sirolimus, tacrolimus, steroids, etc). for at least 8 weeks. The use of rituximab and ibrutinib are not considered IST for this endpoint.

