10.2.2. Secondary Endpoints

Secondary efficacy endpoints:

To estimate:

- Chronic GVHD response (CR + PR, both individual organ response and overall response, according to 2014 NIH Response Criteria Working Group Report) – See Appendix G.
- Cumulative steroid exposure (total mg methylprednisolone or equivalent).
- Time to discontinuation of systemic immunosuppression (defined as the date that all systemic IST has been discontinued after resolution of all reversible manifestations of cGVHD. Discontinuation of immunosuppressive medications for the purpose of inducing an anti-tumor response after the development of recurrent or secondary malignancy will not be counted as successful discontinuation of IST).
- Failure-free survival (defined as being alive without the requirement for second-line cGVHD therapy). See section 6.3 for definition of second-line cGVHD therapy.
- Non-relapse and overall mortality

Safety endpoints:

To estimate:

- Incidence of grade ≥ 3 adverse events, possibly or probably related to either ibrutinib and/or rituximab.

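### The primary endpoint sets no condition on why IST was stopped, so withdrawal for an anti-tumor effect can meet its success criteria, although the secondary discontinuation endpoint excludes such withdrawal

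*Combined protocol and SAP*

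**What the plan says.** **Primary endpoint.** Section 10.2.1: "The primary endpoint is to estimate the proportion of patients that are alive and off all systemic IST at 12 months following initiation of treatment". Section 2.1 agrees: "The primary efficacy endpoint is to estimate the proportion of patients that are alive and off IST at 12 months following initiation of treatment". The synopsis and 2.1 add: "To meet this endpoint, patients need to remain off IST (e.g. sirolimus, tacrolimus, steroids, etc). for at least 8 weeks". Section 10.2.1 words this as: "To meet this endpoint, patients need to remain off IST for at least 8 weeks after discontinuing systemic immunosuppression". The only carve-out is: "The use of rituximab and ibrutinib are not considered IST for this endpoint".

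**Secondary endpoint, time to discontinuation.** Section 10.2.2 (also 2.2 and the synopsis) dates the event from when "all systemic IST has been discontinued after resolution of all reversible manifestations of cGVHD". It then adds: "Discontinuation of immunosuppressive medications for the purpose of inducing an anti-tumor response after the development of recurrent or secondary malignancy will not be counted" as a successful discontinuation. This exclusion appears only within that secondary endpoint.

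**Benchmark.** Section 1.1.2 reports from the earlier rituximab study that, at 12 months, "56% were alive, free of active GVHD, and off all systemic immunosuppression". Section 10.3 uses the same 56% without the condition on active GVHD. It tests 0.55 against 0.75 with 35 patients, one-sided alpha 0.05 and 80% power.

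**The concern.** The authors foresaw that IST may be withdrawn on purpose when a malignancy returns or a second one appears, and judged that this should not be credited as a treatment success. They wrote that judgment into one endpoint and not into the one on which the trial is decided.

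The primary rate is meant to show that the combination controls cGVHD well enough for IST to be stopped. A patient taken off IST because of relapse says nothing about that, yet fits the success definition if alive and still off IST at month 12. The same patient would be a primary success and a secondary non-success. With 35 patients, open-label treatment and no control arm, a few such cases can move the result across the decision boundary. If the classification is left until the data are known, the choice can be influenced by the result.

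**Working it through.** **Step 1. Does any other section settle the classification?**

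| Section | What it provides | Makes relapse a primary failure? |
|---|---|---|
| 2.1, 10.2.1, synopsis | Alive, off all systemic IST at 12 months, off for at least 8 weeks | No |
| 2.2, 10.2.2, synopsis (secondary) | Anti-tumor withdrawal is not a successful discontinuation | For the secondary endpoint only |
| 4.2, criterion 6 | Progressive or recurrent malignancy excluded | At entry only |
| 6.3, 9.1 | Failure or off-study status on new systemic therapy for worsening cGVHD | No |
| 9.2, 12.10 | Withdrawal at the physician's discretion | No |
| 10.1 | All treated subjects are analyzed | No; the patient still needs a classification |
| 10.3 | Possible replacement after withdrawal for reasons unrelated to treatment | No; the patient could be removed but is not scored as a failure |
| 10.4 | Competing risks invoked, without naming the events | No |

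Section 8.2.2 requires the reason for any new IST. No section requires the reason for stopping IST.

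**Step 2. Reproduce the planned sample size.** Inputs from 10.3: p0 = 0.55, p1 = 0.75, one-sided alpha 0.05, power 80%.

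n = [(1.645 × √(0.55 × 0.45) + 0.842 × √(0.75 × 0.25)) / 0.20]² = [(0.8183 + 0.3644) / 0.20]² = 34.97, rounded up to 35. The stated figure reproduces. The classification rule does not enter this formula, so N is unaffected unless p0 changes.

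**Step 3. Decision rule.** The plan gives no cut-off. For an exact one-sided binomial test with n = 35:
- P(X ≥ 24 | 0.55) = 7.3%, above 5%.
- P(X ≥ 25 | 0.55) = 3.5%, so the rule is at least 25 of 35.

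**Step 4. Effect of k patients counted only through anti-tumor withdrawal.** The documents give no rate, so k = 1, 2, 3 is assumed. The true cGVHD-driven success rate is held at 0.55, and the null rate is taken not to include such patients.

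- *Lower figure:* the k patients are a random draw, so some would have succeeded anyway. All k count as successes and the other 35 − k succeed at 0.55. The chance is P(Bin(35 − k, 0.55) ≥ 25 − k).
- *Upper figure:* all would otherwise have failed, so the success probability rises to 0.55 + k/35. The chance is P(Bin(35, 0.55 + k/35) ≥ 25).

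| k | Share of 35 | Raised rate (upper) | Chance of declaring success, lower | Upper |
|---|---|---|---|---|
| 0 | 0% | 0.550 | 3.5% | 3.5% |
| 1 | 2.9% | 0.579 | 4.7% | 7.1% |
| 2 | 5.7% | 0.607 | 6.2% | 12.9% |
| 3 | 8.6% | 0.636 | 8.2% | 21.7% |

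With one such patient, the error stays below 5% under the lower assumption and exceeds it under the upper. With two or more it exceeds 5% under both.

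**The case against.** **The plan is silent; it does not state a rule.** A reader might infer that the protocol deliberately credits relapse-driven withdrawal as a success. No sentence says so. The success classification comes from applying the stated criteria literally. Sections 9.2 and 10.3 also allow such a patient to be withdrawn and possibly replaced, and so never scored. This stands as a limit on the claim. It does not close the gap, because removal is discretionary and is not classification as a failure.

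**The two endpoints were not meant to match.** A reader might call them contradictory. They are defined differently: the secondary endpoint also requires reversible cGVHD to have resolved. Scoring one patient differently on two definitions is not a logical contradiction. What remains is that the plan gives no reason to apply the malignancy exclusion to one endpoint and not the other.

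**The historical comparison may be unbiased.** The description of the 56% in 1.1.2 mentions no malignancy exclusion. If the earlier study counted such patients, the null rate already contains them and the bias shrinks or cancels. Tightening only the new trial would then make it stricter than its benchmark. This stands, and is why the benchmark must be checked as part of the fix.

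**The group is narrow.** The patient must have a recurrent or second malignancy, stop IST early enough to complete 8 weeks off, not restart, and be alive at month 12. A patient who dies before month 12 or is back on IST still fails. This stands, and the documents give no count.

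**Conclusion.** The gap in the definition is certain from the text: the primary endpoint ignores why IST was stopped, and nothing elsewhere makes anti-tumor withdrawal a primary failure. The likely direction is an inflated success rate, by 2.9 percentage points for each patient who would otherwise have failed.

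The size is conditional. It rests on an assumed one to three such patients, a true rate of 0.55, the exact rule derived above, and a null rate that does not already include them. A reader might take the upper figures alone and conclude that two or three such patients raise the false-positive rate to 13% or 22%. The documents do not support that, because nothing shows that all of them would otherwise have stayed on IST. Nor do the documents establish a bias in favor of the combination over rituximab alone, since they do not say how the earlier study classified these patients.

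The classification should be fixed before analysis.

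**What to change.** 1. Add the existing anti-tumor-withdrawal exclusion to the primary endpoint in the synopsis, 2.1 and 10.2.1.
2. State that these patients stay in the all-treated denominator as non-successes and are not replaced under 10.3.
3. Record the reason for every IST stop on the CRF.
4. Report the number of patients reclassified, and give the primary result under both classifications as a sensitivity analysis.
5. Check that the 56% benchmark is computed under the same definition, both for malignancy-driven withdrawal and for the condition of being free of active GVHD given in 1.1.2 but absent from 10.2.1 and 10.3.

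Cost: one sentence in three places, a line in 10.3, one CRF field and a re-check of the earlier study's data. The reported success rate may be slightly lower. N stays at 35 unless the benchmark changes.

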10.2.2. Secondary Endpoints

Secondary efficacy endpoints:

To estimate:

- Chronic GVHD response (CR + PR, both individual organ response and overall response, according to 2014 NIH Response Criteria Working Group Report) – See Appendix G.
- Cumulative steroid exposure (total mg methylprednisolone or equivalent).
- Time to discontinuation of systemic immunosuppression (defined as the date that all systemic IST has been discontinued after resolution of all reversible manifestations of cGVHD. Discontinuation of immunosuppressive medications for the purpose of inducing an anti-tumor response after the development of recurrent or secondary malignancy will not be counted as successful discontinuation of IST).
- Failure-free survival (defined as being alive without the requirement for second-line cGVHD therapy). See section 6.3 for definition of second-line cGVHD therapy.
- Non-relapse and overall mortality

Safety endpoints:

To estimate:

- Incidence of grade ≥ 3 adverse events, possibly or probably related to either ibrutinib and/or rituximab.

10.2.3. Exploratory Endpoints

Biomarkers:

B-cell numbers and subsets, T cell numbers and subsets, T regulatory cells, serum BAFF levels and serum cytokine levels will be measured at baseline, months 1, 2, 3, 6, 9, and 12 to explore biomarkers which predict cGVHD response.

10.3. Sample Size Determination

The study will be powered to detect a clinically meaningful improvement in treatment success at 12 months post-treatment, defined as being alive and off systemic immunosuppression.

Experience from our phase II study of rituximab in the upfront treatment of cGVHD found that 56% of patients were alive and off systemic immunosuppression at 12 months post treatment. It is hoped that under this protocol, this rate will be at least 75%. Thus we statistically formalize this study by testing the null hypothesis that p , the treatment success rate is 0.55 or less versus the alternative hypothesis that p is at least 0.75. A sample size of 35 patients gives 80% power with an alpha=0.05, using the formula for a one sample binomial (one-sided) test of a proportion. Replacement of subjects may be possible for those who are lost to follow-up or withdraw from study before 12 months due to non-treatment related reasons, in order to ensure statistical power of the study.

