Statistical Methods/ Data Analysis: Refer to Section 10 for additional details.	
This is a phase II trial evaluating the safety and efficacy of ibrutinib and rituximab as primary treatment of cGVHD. We plan to enroll 35 patients on this study. Patients will be formally monitored for 12 months to evaluate for outcome and safety endpoints. All patients, responders and treatment failures, will be followed for a period of one year. The primary outcome measure will be the proportion of patients that are alive and off systemic immunosuppression therapies (IST) at 12 months following initiation of treatment. Secondary outcome measures will be cGVHD response, cumulative steroid exposure, time to discontinuation of systemic immunosuppression, requirement for second-line GVHD therapy, non-relapse and overall mortality, and safety.

Sample Size Determination	
The study will be powered to detect a clinically meaningful improvement in treatment success at 12 months post-treatment, defined as being alive and off all systemic immunosuppression. Experience from our phase II study of rituximab in the upfront treatment of cGVHD found that 56% of patients were alive and free of systemic immunosuppression at 12 months post treatment. It is hoped that under this protocol, this rate will be at least 75%. Thus we statistically formalize this study by testing the null hypothesis that p, the treatment success rate is 0.55 or less versus the alternative hypothesis that p is at least 0.75. A sample size of 35 patients gives 80% power with an $\alpha=0.05$, using the formula for a one sample binomial (one-sided) test of a proportion.

----------------------------------	--

ABBREVIATIONS

AE	adverse event
AESI	adverse events of special interest
ALT	alanine aminotransferase
ANC	absolute neutrophil count
ASCO	American Society of Clinical Oncology
AST	aspartate aminotransferase
AUC	area under the concentration-time curve
BCR	B-cell receptor
BTK	Bruton's tyrosine kinase
CLL	chronic lymphocytic leukemia
C _{max}	maximum observed plasma concentration
CR	complete response
CrCl	creatinine clearance
CRF	case report form (paper or electronic as appropriate for this study)
CT	computed tomography
CTCAE	NCI Common Terminology Criteria for Adverse Events
CYP	cytochrome P450
DMC	Data Monitoring Committee
ECOG	Eastern Cooperative Oncology Group
ECG	electrocardiogram
EDC	electronic data capture
FDA	Food and Drug Administration
GCP	Good Clinical Practice

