8.2.2. Response Follow-up

Required testing for the response follow-up visits (months 1, 2, 3, 6, 9, 12):

- Medical history
- Physical examination, including vital signs, weight, and Karnofsky performance status
- Laboratory evaluation per institutional guidelines including CBC with differential, glucose, BUN, creatinine, total bilirubin, alkaline phosphatase, LDH, albumin, SGOT(AST), SGPT (ALT), CRP, CK, calcium, and magnesium.
- Biomarkers (correlative lab studies)
- Documentation of concomitant medications
- Completion of institutional GVHD assessment form (see Appendix E)
- Completion of a GVHD patient self-report form (see Appendix F)
- Document cumulative corticosteroid use
- Document any new systemic IST and reason for use

- Document treatment-emergent toxicities and adverse events
- Document any IVIG use
- PFTs (at 3, 6, 9 and 12 month visits only)

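### The null rate of 0.55 is not shown to be the rituximab-alone rate on this trial's primary endpoint: the historical 56% carries a GVHD condition that the endpoint lacks, and the endpoint carries an undated 8-week rule

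*Combined protocol and SAP*

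**What the plan says.** - **Section 1.1.2** summarises the institution's phase II study of upfront rituximab in 25 patients. At 12 months from treatment start, "56% were alive, free of active GVHD, and off all systemic immunosuppression". It also reports: "Immunosuppression was discontinued in 17 of 22 evaluable patients (77%) with median time to discontinuation of 300 days".
- **Section 10.3** says the same study "found that 56% of patients were alive and off systemic immunosuppression at 12 months post treatment". The synopsis says "56% of patients were alive and free of systemic immunosuppression at 12 months post treatment". Neither mentions GVHD activity. Both go straight on to a null of 0.55 or less against an alternative of at least 0.75, with 35 patients, 80% power and one-sided alpha 0.05.
- **Section 10.2.1** defines the primary endpoint as being alive and off all IST at 12 months, and adds that "patients need to remain off IST for at least 8 weeks after discontinuing systemic immunosuppression". Section 2.1 and the synopsis carry the same rule. None gives a date by which the 8 weeks must be complete.
- **Sections 2.2 and 10.2.2** and the synopsis mention resolution of reversible cGVHD manifestations, but only within the secondary endpoint of time to discontinuation of IST.
- **Section 2.1** states the primary objective as efficacy "versus the historical experience with rituximab alone in the upfront treatment of cGVHD".

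**The concern.** In a single-arm trial the null rate stands in for the control group. Here it rests on one historical figure, and the documents describe that figure in two ways. Neither description matches the endpoint that will be compared with it. If 0.55 is not the rituximab-alone rate on this endpoint, part of any difference from 0.55 may come from how success is defined rather than from ibrutinib. If the true benchmark is higher, the trial declares success too easily. If it is lower, the trial is too strict and may miss a real gain.

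**Working it through.** **1. The plan's own figure.** Inputs from section 10.3: p0 = 0.55, p1 = 0.75, one-sided alpha 0.05 (z = 1.645), power 80% (z = 0.8416).

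N = [(1.645·√(0.55·0.45) + 0.8416·√(0.75·0.25)) / 0.20]² = 34.97, rounded up to 35.

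The sample size reproduces, so the arithmetic is not at issue.

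**2. The definitions side by side.**

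| Component | 56% in 1.1.2 | 56% in 10.3 and synopsis | Primary endpoint (10.2.1) |
|---|---|---|---|
| Alive at 12 months | yes | yes | yes |
| Off systemic IST | yes | yes | yes |
| No active GVHD | yes | not mentioned | not stated |
| At least 8 weeks off IST | not mentioned | not mentioned | yes, no completion date |

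**3. Direction.** Dropping the GVHD condition leaves the historical rate at 56% or raises it. Imposing an 8-week rule leaves it or lowers it, the former if the 56% already met such a rule. The documents give no figure for either effect, so the net direction cannot be derived.

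**4. Why the completion date could matter.** If the 8 weeks must end by day 365, IST must stop by day 365 − 56 = 309. The historical median stop (among those who stopped) was day 300, only nine days before that. If the 8 weeks may start as late as day 365, they end at day 365 + 56 = 421.

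**5. Illustration of size.** The documents do not give the historical rate on this endpoint, so the rates 0.52 and 0.60 are assumed. They are 4 points either side of 0.56, which is one patient in 25 (1/25 = 0.04). The rule of 25 or more successes in 35 is the smallest exact cut-off with one-sided alpha at or below 0.05 when p0 = 0.55. The plan does not state it, and section 10.4 names Kaplan-Meier and log-rank methods instead.

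| Rituximab-alone rate on this endpoint | P(X ≥ 25 of 35) if the combination is no better | Exact cut-off if p0 is reset to it (alpha) | Power at 0.75, N = 35: exact / normal approximation |
|---|---|---|---|
| 0.52 | 1.5% | 24 (3.5%) | 85.8% / 89.3% |
| 0.55 | 3.5% | 25 (3.5%) | 75.8% / 80.0% |
| 0.56 | 4.6% | 25 (4.6%) | 75.8% / 76.1% |
| 0.60 | 11.2% | 27 (2.6%) | 47.4% / 57.5% |

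Part of the exact fall at 0.60 is discreteness: 26 or more has alpha 5.75%, which forces the cut-off to 27. On the other side, if the true rate is 0.52 and p0 stays at 0.55, the plan's own 20-point gain (to 0.72) succeeds with probability P(X ≥ 25 | 0.72) = 61%.

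**6. Precision of the benchmark.** 14/25 = 0.56 is the likely count but is inferred; 9/16 and 10/18 also round to 56%. If it is 14/25, the exact 95% confidence interval is 35% to 76%.

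**The case against.** The case on the other side has real force, and it limits the point in several ways.

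- **A reader might infer that section 10.3 misstates the historical result.** That is not proven. If every historical patient off IST at 12 months was also free of active GVHD, both wordings describe the same patients. What the documents show is an omitted condition that needs reconciling.
- **A reader might infer that the 56% was counted without a durability rule**, for instance because some recurrences in the historical cohort came soon after stopping IST. Section 1.1.2 is a short summary, and its silence shows nothing either way. The recurrence figures describe patients who had stopped IST, not the patients who make up the 56%.
- **A reader might carry the secondary definition over to the primary endpoint**, so that stopping IST already implies resolved cGVHD. The documents attach that wording only to time to discontinuation. It concerns the moment of stopping, not status at month 12, so it does not close the gap.
- **A reader might call the GVHD condition immaterial because section 3.1 delays taper until cGVHD is quiescent.** That rule governs this trial. Section 1.1.2 gives no taper rule for the historical cohort.
- **A reader might infer that no IST data exist after month 12.** Scheduled visits do end there (8.2.2, Appendix A), but section 7.1.1.4 records all medications to 30 days after the last dose of study drug. If that means ibrutinib only, without holds, recording ends at about 12 × 28 + 30 = day 366. If it includes the month-13 rituximab dose (3.1), it ends at about day 365 + 30 = 395 or 395 + 30 = 425, depending on whether month 13 is counted from its start or its end. Whether that reaches day 421 is unclear.
- **The size is assumed.** At the quoted 56% the false-positive rate is 4.6%, within the nominal 5%, and the benchmark's own sampling interval is far wider than 4 points.

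What survives is the comparability gap itself: no section derives the historical rate on the definition that the trial will use.

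**Conclusion.** The point holds as one of comparability. The 0.55 null is not shown to be the rituximab-alone rate on the primary endpoint, because the source figure carries a GVHD condition that the endpoint lacks, and the endpoint carries an 8-week rule that no description of the figure mentions. The documents do not support saying that 0.55 is too high or too low, nor that N = 35 is miscalculated.

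The textual difference is certain; its effect is not. One historical patient reclassified either way (assuming a denominator of 25) would put the false-positive rate of the implied exact rule at 1.5% or 11.2%, against 3.5% at 0.55. These figures rest on the assumed rates and on a success rule that the plan does not state. The gap deserves fixing because this is the only stated basis for the null of a single-arm trial and it is cheap to close.

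**What to change.** 1. Bring section 10.3 and the synopsis into line with section 1.1.2, after confirming the numerator and denominator of the 56% from the historical report.
2. In section 10.2.1 (and 2.1 and the synopsis), state when the 8 weeks off IST must be complete. If they may run past month 12, say explicitly that IST status is collected to that date.
3. Re-score the roughly 25 historical patients on that exact definition from the institution's records, by a rule fixed in advance and without reference to this trial's outcomes. Set p0 to the resulting rate, or justify 0.55 against it, in a dated amendment before outcomes are reviewed. If outcomes are already known, which is possible in an open-label trial, keep 0.55 as the formal null and report the comparison with the re-scored rate as a sensitivity analysis.
4. Restate the success rule and the power at N = 35 for the p0 used. A larger N is not required; a lower power can simply be stated.

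**Cost:** a small record review, one amendment and a few wording changes. The stated power may fall. Re-scoring removes the mismatch in definition but not the sampling error of a benchmark from about 25 patients.

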3.2. Study schema

4. SUBJECT SELECTION

4.1. Inclusion Criteria

Prior to enrollment, each potential subject must satisfy all of the following inclusion criteria:

1. First episode of systemic immunosuppression-requiring cGVHD, defined as classic or overlap cGVHD by the NIH consensus criteria.
2. Previously untreated cGVHD, defined by having received <10 days of corticosteroids or alternative systemic immunosuppressive agent started specifically for a new diagnosis of cGVHD
3. Age ≥ 18 years
4. Karnofsky performance status $\geq 70\%$
5. Patient willing and able to provide informed consent
6. Adequate hematologic function defined as:
 - Absolute neutrophil count (ANC) $\geq 1.0 \times 10^9/L$ and off growth factor support for 7 days.
 - Platelet count $\geq 30 \times 10^9/L$ and no platelet transfusions for 7 days.
7. Adequate hepatic function as defined by:
 - Total bilirubin of $\leq 1.5 \times$ ULN (unless of non-hepatic origin or due to Gilbert's Syndrome) or
 - Total bilirubin of $> 1.5 \times$ ULN to $3.0 \times$ ULN if due to cGVHD.
8. Women of childbearing potential and men who are sexually active with a woman of childbearing potential must be practicing a highly effective, preferably user-independent method of birth control (failure rate of $<1\%$ per year when used consistently and correctly)

during treatment and for up to 90 days after the last dose of ibrutinib, consistent with local regulations regarding the use of birth control methods for subject participating in clinical studies.

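### Rejecting the fixed 55% null in 10.3 does not show benefit over rituximab alone: read that way, the false-positive rate averages about 13%, and 10.4 leaves the historical comparison undefined

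*Combined protocol and SAP*

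**What the plan says.** Section 2.1 states the primary objective as a comparison: "to evaluate the efficacy of the combination of rituximab and ibrutinib versus the historical experience with rituximab alone in the upfront treatment of cGVHD".

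Section 10.3 turns this into a one-sample, one-sided binomial test whose null is that "the treatment success rate is 0.55 or less versus the alternative hypothesis that" the rate is at least 0.75. It adds: "A sample size of 35 patients gives 80% power with an alpha=0.05". The 0.55 is the 56% observed at 12 months in the centre's earlier rituximab study, rounded down.

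Section 1.1.2 describes that study. It enrolled 25 patients, and at 12 months "56% were alive, free of active GVHD, and off all systemic immunosuppression". The protocol gives no interval for the 56%, and 10.3 makes no allowance for its sampling error.

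Section 10.4 does not mention the binomial test. It says the primary endpoint will be estimated by Kaplan-Meier methods and compared with historical values by a log rank test. It does not say whether those values are the earlier patients' individual data or a fixed figure.

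**The concern.** A test against a fixed 0.55 answers whether the success rate exceeds 55%. The objective asks whether adding ibrutinib does better than rituximab alone. The two questions coincide only if the rituximab rate is known to be 55%, and an estimate from 25 patients does not establish that. If the true rituximab rate is higher, the trial can pass with no contribution from ibrutinib.

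What is at stake is the wording of the main conclusion. A positive result reported as an improvement on rituximab alone would carry an error rate above the stated 5% and an interval that omits half of the uncertainty. Because 10.4 leaves its comparison undefined, the plan does not settle whether the historical error is carried.

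**Working it through.** **Inputs.** p0 = 0.55, p1 = 0.75, one-sided alpha 0.05, power 80%, N = 35 (10.3). Historical rate 56% (10.3, 1.1.2). Historical sample 25 (1.1.2). The count is not printed. 0.56 × 25 = 14 exactly, and no count out of the 22 evaluable patients also mentioned in 1.1.2 rounds to 56% (12/22 = 54.5%), so 14/25 is assumed.

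**1. The plan's own figure.** N = [(1.645·√(0.55·0.45) + 0.842·√(0.75·0.25)) / 0.20]² = [(0.818 + 0.364)/0.20]² = 34.97, so 35. Power at 35 by this approximation is 80.0%. The figure reproduces.

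**2. The exact rule.** With X ~ Bin(35, p), P(X ≥ 24 | 0.55) = 7.3% and P(X ≥ 25 | 0.55) = 3.5%. Success therefore needs at least 25/35. Exact alpha is 3.5% and exact power at 0.75 is 75.8%.

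**3. Uncertainty in the benchmark.** The Clopper-Pearson 95% CI for 14/25 is 34.9% to 75.6%. It includes the 75% target.

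**4. Chance of passing if ibrutinib adds nothing**, P(X ≥ 25 | 35, p), by true rituximab rate p:

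| True rate | P(pass) |
|---|---|
| 0.45 | 0.1% |
| 0.50 | 0.8% |
| 0.55 | 3.5% |
| 0.56 | 4.6% |
| 0.60 | 11.2% |
| 0.65 | 27.2% |
| 0.70 | 51.0% |

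Averaged over the posterior for the rituximab rate given 14/25 (beta-binomial):
- Beta(15, 12), uniform prior: 12.6%
- Beta(14.5, 11.5), Jeffreys prior: 13.3%

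A repeated-sampling check draws 25 and 35 patients from the same true rate of 0.55 and sets the null at whatever the historical sample shows. It gives 12.2% with the exact cut-off and 14.2% with the normal cut-off.

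**5. A just-positive result set against the historical sample.** 25/35 − 14/25 = 71.4% − 56.0% = 15.4 points. Wilson 95% limits are 54.9% to 83.7% for 25/35 and 37.1% to 73.3% for 14/25. The Newcombe interval combines them:
- Lower: 0.154 − √[(0.714 − 0.549)² + (0.733 − 0.560)²] = −0.085
- Upper: 0.154 + √[(0.837 − 0.714)² + (0.560 − 0.371)²] = 0.380

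One-sided Fisher p = 0.17. It first falls below 0.05 at 28/35 (p = 0.044).

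**6. If 10.4 means a two-sample comparison on patient data.** A two-proportion approximation with 25 and 35 patients, one-sided 0.05, 0.55 versus 0.75:
- pooled rate (25·0.55 + 35·0.75)/60 = 0.667
- null SE √[0.667·0.333·(1/25 + 1/35)] = 0.1234
- alternative SE √[0.55·0.45/25 + 0.75·0.25/35] = 0.1235
- power Φ[(0.20 − 1.645·0.1234)/0.1235] = 49%

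Starting from 0.56 instead of 0.55 gives 46%.

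**The case against.** **Fixed benchmarks are normal in single-arm phase II trials, and the test is valid for its stated null.** This stands. Exact alpha is 3.5%, and nothing here argues against the one-sample test as a decision rule. A reader might infer that the trial's type I error is wrong or that the protocol claims superiority. The documents support neither. They do not use that word, and they do not commit to reporting rejection as a win over rituximab alone. The comparative objective, together with 10.3's aim of detecting an improvement, does invite that reading.

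**Section 10.4 may already carry the historical error.** The earlier study was run at the same institution, so a log rank test on its patient data is plausible. On that reading alpha is not inflated in this way, and the problem becomes power of roughly 46% to 49%. If the historical value is a fixed figure, the inflation applies. The text does not settle which is meant.

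**The true rate may be lower than 0.55.** It may. Under the Jeffreys posterior about 46% of the probability lies at or below 0.55, where the error is at most 3.5%; only about 7% lies above 0.70. The 27% and 51% rows are therefore not typical, and the average of about 13% is the fair summary.

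**The populations differ.** The earlier cohort was "without residual or concurrent acute GVHD", whereas this trial accepts disease "defined as classic or overlap cGVHD by the NIH consensus criteria". A reader might infer a biased benchmark. However, 4.2 excludes late persistent or recurrent acute GVHD, which narrows the gap, and the documents give no direction for any bias. This difference plays no part in the figures above.

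**Conclusion.** The concern holds for the comparative conclusion, not for the test itself. Rejecting p ≤ 0.55 supports a success rate above 55%. Read as better than rituximab alone, the same rejection has a false-positive rate of about 13% on average (12.6% to 13.3% by prior), and the smallest positive result is compatible with no difference from 14/25.

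This assumes that the 56% is 14/25, that success is declared at 25/35 or more, and that the historical value is treated as fixed. If 10.4 intends a patient-level comparison, the inflation goes but the 80% power does not apply to it.

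The figures cover sampling error only. They do not reflect the endpoint mismatch: per 1.1.2 the historical 56% also required freedom from active GVHD, whereas the new endpoint (10.2.1) does not, and instead requires at least 8 weeks off systemic immunosuppression.

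**What to change.** In 10.3 and 10.4:

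1. Name the one-sample exact binomial test (success at 25/35 or more) as the single primary test, and remove the log rank test as the primary comparison. State its exact operating characteristics at N = 35: alpha 3.5%, power 75.8%. State that rejection will be reported as a success rate above the fixed 55% benchmark, not as better than rituximab alone.
2. Beside it, report the difference from 14/25 with a 95% Newcombe interval, after confirming the count, and base any statement about rituximab alone on that interval. Note that it carries sampling error only and that the two endpoints are defined differently. If the historical patient data are available, score both cohorts on one definition instead.

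A further comparison restricted to classic cGVHD is not worth adding: its size within 35 patients is unknown and it would be very imprecise.

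The cost is SAP wording and one table row, with no added patients. The permitted claim becomes less favourable.
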